Risk stratification systems are established tools in medicine, including in sub-Saharan Africa(16,17), to predict mortality in paediatric inpatients(18) and neonates(19), but previously tested systems for prediction of neonatal sepsis in low-resource settings show modest performance(20). This may be due to limited laboratory testing, so systems are built at least partially on clinician defined sepsis rather than the gold-standard of blood culture diagnosis(20). In high resource settings, risk stratification systems have focused on reducing overtreatment and antibiotic resistance(14,15,21). Neonatal sepsis risk calculators (a risk stratification system with a digital interface), such as the Kaiser Permanente (KP) Early-Onset Sepsis (EOS) calculator, have been adopted in the USA and UK(22). This calculator uses local incidence of EOS, gestational age, time from rupture of membranes (ROM) to delivery, highest maternal temperature during labour, maternal group B Streptococcus status, and type and timing of antepartum antibiotics(23).

In low-resource settings, the consequences of missing neonatal sepsis are more severe due to limited higher acuity care(24). Therefore, sepsis risk assessment in a low-resource setting should prioritise sensitivity over specificity, although prioritisation of limited resources for true cases is also helpful(25). Existing risk calculators may be inappropriate to use in a

Using machine learning to model early-onset neonatal sepsis risk in Uganda (NeoRisk)

low-resource setting; background incidence of EOS is much higher in these settings(1,2). Other clinical and non-clinical factors may mediate risk, such as HIV status or birth location. Few of the usual risk factor inputs are available in a low-resource setting. For example, without adequate antenatal care and imaging, gestational age may be uncertain, and without skilled birth attendants, duration of ROM may be unknown. Finally, diagnostic facilities for sepsis such as biochemical tests for inflammatory markers may be limited or unavailable. This makes identification of those at-risk using clinical factors, as opposed to laboratory testing, even more important. Additionally, lack of access to blood cultures has limited the ability of previous models to include this 'gold standard' of diagnosis in their modelling(20).

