4.2 Outcome

- Primary outcome for Phase 1: Positive blood culture amongst neonatal participants
- Primary outcome for Phase 3: Clinician (specialist neonatal or paediatric doctor) diagnosis of sepsis amongst neonatal participants as documented in clinical notes or discharge letter
- Clinical features of neonatal sepsis as listed in GAIA neonatal infections case definition
- Admission to neonatal unit
- Readmission to hospital in first 28 days amongst neonatal participants
- Death before 28 days of age
- Sensitivity, specificity, positive and negative predictive value of risk stratification model for participants in Kampala and Harare

Using machine learning to model early-onset neonatal sepsis risk in Uganda (NeoRisk)

5 STUDY DESIGN and METHODS of DATA COLLECTION AND DATA ANALYSIS

There will be three main phases to this study, which is an observational cohort study.

Using machine learning to model early-onset neonatal sepsis risk in Uganda (NeoRisk)

Phase 1 will take place at Kawempe Hospital in Kampala, Uganda. Participants will be recruited from labour wards by study staff, and interim analysis will be completed after recruitment of 10% of the total sample. See section 7.3 for further details.

Data will be collected via an online CRF, including the factors listed in the table in Section 3.

Additionally:

- All neonates within the study will have a **neonatal venous blood sample** taken for culture by designated study staff
 - This must be taken before administration of antibiotics or within 48 hours of birth, whichever is sooner, and regardless of whether the neonate is being investigated and treated for sepsis.
- **Postnatal information** will be collected via telephone at 1 month including maternal and infant outcome, hospital readmission or clinical illness, and vaccines given

All data will be checked for quality control by a member of the study team.

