The focus groups will be conducted by members of MUJHU's social sciences team and [name]. A tool has been developed by the social sciences team and [name] for these discussions (see attached). The discussions will be recorded, and recordings destroyed once the discussions have been transcribed. The social sciences team will then complete thematic analysis of the discussions.

We anticipate Phase 1 will take place between January and July 2024.

Phase 2 will use the data collected in phase 1 to construct a risk stratification model, in collaboration with the Advanced Research Computing Centre at University College London.

We anticipate Phase 2 will take place between March and September 2024.

Using machine learning to model early-onset neonatal sepsis risk in Uganda (NeoRisk)

Phase 3 will involve external validation of the risk stratification tool. This phase will take place at Sally Mugabe Central Hospital in Harare, Zimbabwe. Participants will be recruited from antenatal clinics and labour wards by study staff.

The same data will be collected from participants in Phase 3 as in Phase 1. Ideally, data collection will take place via the Neotree platform(41) – this will be decided once the factors included in the model have been determined, and whether they are already in routine collection via Neotree. If the Neotree platform will not capture sufficient data to match the inputs of the model, an online CRF will be created as in Phase 1 via REDCap. This decision will be made in collaboration with the local study team prior to the start of recruitment.

The primary outcome for Phase 3 will be senior clinician diagnosis of sepsis recorded within 48 hours of delivery, and blood cultures (when available) will only be taken in neonates judged to be at risk of, or with clinical signs of sepsis as per standard clinical guidelines. Using senior clinician diagnosis of sepsis as the outcome is because supply of blood culture bottles and laboratory analysis of cultures is unreliable and is unlikely to be available to all study participants as in the Phase 1 setting. The risk stratification model will be applied to these data to determine its accuracy in a second population and explore its generalisability.

We anticipate Phase 3 will take place between September 2024 and March 2025.

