The TRIPOD (Transparent reporting of a multivariable prediction model for individual prognosis or diagnosis) statement have been followed in the design of this study and will be followed in its reporting(42). Adjustments will be made as necessary with the release of upcoming artificial intelligence-specific guidelines.

Data analysis

Phase 2 will constitute the main data analysis for data from Uganda.

There will be two main streams to data analysis, which will be completed using R and in collaboration with the Advanced Research Computing Centre at UCL.

1. Machine learning analysis:
 - a. Data from Phase 1 will form a ‘training data set’, with 20% reserved for testing and validation, and be fed into a pre-programmed machine
 - b. Previous methods used for sepsis prediction that will be investigated include gradient tree boosting and neural networks
 - c. Bootstrapping will be considered
 - d. Determination of the exact machine learning model will depend on the data obtained, but the following will be considered:
 - i. Weighted inputs: Allows scaling of measurements
 - ii. Conformal prediction: Allows the machine to determine how uncertain its prediction is, based on distribution of data it has, and missing data
 - iii. Recurrent neural networks: Allows the machine to recognise time-dependent patterns
 - iv. Gradient descent: A method of ‘training’ a machine to minimise the error between prediction and reality by gradually adjusting its weights
2. Traditional logistic regression will be used to identify risk factors associated with clinical and microbiological diagnoses of neonatal sepsis. Although the principal model will be created using machine learning techniques, logistic regression will be

Using machine learning to model early-onset neonatal sepsis risk in Uganda (NeoRisk)

used as a second check of results and to provide additional context with which to interpret the machine learning model

For **Phase 3**, data will be inputted to the machine learning model from Phase 2, and the sensitivity, specificity, positive predictive and negative predictive values calculated, as well as the AUC value.

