7.2 Sampling

7.2.1 Size of sample

Phase 1: There is currently no accepted way to power a machine learning study, the consensus being that more data will always create a better model. However, to ensure the success of this study, we have investigated approximate power to create a diagnostic test to estimate the sample size needed for this study. We have also reviewed this sample size calculation with our collaborators at the UCL Advanced Research Computing centre.

A study of a diagnostic test with 90% sensitivity and a background sepsis rate of 5% (the estimated rate of culture-positive sepsis in Kampala based on previous studies is 12.8%(13) amongst those with clinical signs of sepsis, and up to 5% amongst all neonates according to unpublished data from previous studies at Kawempe) would require 1460 participants (95% confidence interval), as described by Buderer and Jones *et al*(45,46).

This sample size has also been calculated according to three suggested methods for calculating the sample size for a clinical prediction model:

- Calculation of size needing to provide precise estimate of overall outcome risk
- Calculation of size needed to produce predicted values with a small mean error across all individuals
- Size needed considering shrinkage of predictor effects

All of the above methods produced sample sizes from 140-1532, hence the size of 1600 should be sufficient even with some loss to follow up. If, at interim analysis, the rate of culture-positive sepsis is significantly lower, we will explore methods to increase our sample size such as using existing data to create simulated data to train our model.

Phase 3: The sample size will be 900 mothers; this is powered to give 95% confidence for a diagnostic test which has 90% sensitivity with a background rate of clinical sepsis of 16%, using the same calculation method as for the sample size in Phase 1. Although there are limited previous studies of neonatal sepsis prevalence in Zimbabwe using blood cultures, particularly amongst all neonates, one study found a culture-positive sepsis rate of 21% amongst NICU admissions(47), and a recent study reported a clinical diagnosis rate of 40.8%(48) . Therefore, this sample size should give an estimated 367 episodes of clinician-diagnosed sepsis, deemed by Collins *et al.* to be sufficient for external validation of a prognostic model(49).

Using machine learning to model early-onset neonatal sepsis risk in Uganda (NeoRisk)

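### The Phase 1 sensitivity calculation uses an undivided sample (about 73 cases), but the only internal test the plan commits to is a 20% hold-out with about 16 expected cases at most

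*Combined protocol and SAP*

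**What the plan says.** **Sample size (7.2.1, Phase 1).** For a diagnostic test with 90% sensitivity and a 5% sepsis rate, the plan says the study "would require 1460 participants (95% confidence interval"). The 5% is described as "up to 5% amongst all neonates according to unpublished data from previous studies at Kawempe". No half-width is given and no split of the sample is mentioned. The section then adds: "This sample size has also been calculated according to three suggested methods for calculating the sample size for a clinical prediction model". It concludes: "All of the above methods produced sample sizes from 140-1532, hence the size of 1600 should be sufficient".

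**Analysis (section 5, Data analysis, item 1).** Item 1a treats Phase 1 as the training set, "with 20% reserved for testing and validation, and be fed into a pre-programmed machine". Item 1c leaves bootstrapping as an option, without committing to it. Cross-validation is not mentioned. Logistic regression (item 2) is a check on the results and context for reading them, not a test of the machine learning model on unseen infants.

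**Outcome (4.2).** The listed outcomes include: "Sensitivity, specificity, positive and negative predictive value of risk stratification model for participants in Kampala and Harare". The section does not say in which Phase 1 infants the Kampala figures are to be calculated.

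**Phase 3 (section 5).** The external test uses a different reference: "The primary outcome for Phase 3 will be senior clinician diagnosis of sepsis recorded within 48 hours of delivery". Blood cultures there are limited to infants judged at risk or showing signs, when supplies allow.

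**The concern.** The sample size section and the analysis section appear to describe two different studies of sensitivity. One uses every Phase 1 infant. The other, as far as the text goes, uses a fifth of them. The width of an interval for sensitivity depends on the number of cases, so a fivefold loss of cases makes it a little over twice as wide.

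This matters because Phase 1 is the only part of the study with a culture from every infant, and so the only place where the model can be tested against culture in an unselected group. Section 1 also says that "sepsis risk assessment in a low-resource setting should prioritise sensitivity over specificity". That sentence concerns where to set the operating point, not precision, but it makes sensitivity the figure that readers will look to. An interval from about 62% to 98% cannot separate a model that misses more than a third of cases from one that misses almost none. A reader of 7.2.1 is not told that this is the likely precision.

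**Working it through.** **Inputs.** From 7.2.1: sensitivity 0.90, culture-positive rate 0.05 (an upper value), 1460 required, 1600 planned, range over all methods 140 to 1532. From section 5, item 1a: 20% reserved. I take the 95% interval as two-sided (z = 1.96).

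**1. The plan's own figure.** The usual precision formula is N = z² × Se × (1 − Se) / (W² × prevalence), where W is the half-width. W is not stated, so 1460 cannot be reproduced directly. Working backwards:
- Cases: 1460 × 0.05 = 73.
- W = 1.96 × √(0.9 × 0.1 / 73) = 0.0688, or about 7 points.
- Forward check with W = 0.07: 70.56 cases, giving 1412 infants, or 1420 if cases are rounded up to 71. W = 0.06 gives 1921 and W = 0.08 gives 1081.

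So 1460 fits a half-width of about 7 points on an undivided sample.

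**2. Cases in the hold-out.**
- 0.20 × 1600 = 320 infants, and 320 × 0.05 = 16 expected cases.
- All of Phase 1: 1600 × 0.05 = 80 expected cases.
- Unless the split is stratified by outcome, the hold-out count varies. The 2.5% and 97.5% points of Binomial(320, 0.05) are 9 and 24.

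**3. Precision on the same base of 1600 infants.** The normal half-width at 90% sensitivity is 1.96 × √(0.09 / n):
- n = 80: 6.6 points.
- n = 16: 14.7 points, a ratio of √(80/16) = 2.2.

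The half-width serves only for comparison, since 90 + 14.7 exceeds 100%. Exact (Clopper-Pearson) 95% intervals are the ones to report:

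| Detected / cases | Estimate | Exact 95% interval |
|---|---|---|
| 14/16 | 87.5% | 61.7% to 98.4% |
| 15/16 | 93.8% | 69.8% to 99.8% |
| 72/80 | 90.0% | 81.2% to 95.6% |

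The 72/80 interval is a best case. An optimism-corrected or cross-validated estimate carries further uncertainty that a simple binomial interval leaves out.

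**4. Why 16 is the upper end of what to expect.** The 5% is an upper value. At 4%, 3% and 2% (my assumptions) the hold-out would have 12.8, 9.6 and 6.4 expected cases. The 20% also covers both testing and validation, so a separate tuning set would leave fewer test cases.

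**5. What a hold-out of the 7.2.1 size would need.** To place 73 cases in a 20% hold-out takes 73 / 0.05 / 0.20 = 7300 infants.

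**6. Training set.** 0.80 × 1600 = 1280. The largest size in 7.2.1 is 1532. The diagnostic method gave 1460, so 1532 must come from one of the three prediction-model methods. The shortfall would be 1532 − 1280 = 252 infants (1280/1532 = 84%). The plan does not say which method gave 1532:
- If it was the mean-error or shrinkage method, the figure concerns model development and the 1280 training infants fall below it.
- If it was the overall-risk method, all 1600 infants can serve that estimate and the split does no harm.

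**7. Phase 3, for comparison.** 900 × 0.16 = 144 cases at the rate used to size it, giving a half-width of 4.9 points, but against clinician diagnosis.

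**The case against.** The strongest reply is that the central link is inferred. No sentence says that Kampala sensitivity will be estimated in the 20%. Bootstrapping stays open, and the exact model is left to depend on the data. What the documents show is an analysis set that is not named. This stands, and it is why the conclusion is conditional. The alternatives do not rescue the text, though. Sensitivity in the training infants would be optimistic and would leave the reserve without a purpose, and resampling is not committed to.

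A second reply is that 7.2.1 offers 1460 only as an approximate guide and promises no half-width. This also stands. A reader might infer that the hold-out breaks a stated precision target. It does not, because there is no such target, and the 7 points are back-calculated.

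Third, section 3 presents testing in a second population as the planned answer to the need for external data, and Phase 3 has its own sizing. That is a fair account of the design, and the plan explains why clinician diagnosis is used there. It still leaves no other culture-based estimate in all infants.

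Fourth, 7.2.1 has a contingency for a lower culture-positive rate at the interim analysis. Its only example is simulated data for training, which would not add real cases to a test set.

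Finally, a hold-out is a legitimate choice, and resampling gives up a single untouched Ugandan test set. That cost is real. It is limited, because Phase 3 remains as an independent test.

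**Conclusion.** The point holds in conditional form, with medium confidence. The sensitivity calculation in 7.2.1 assumes an undivided sample with about 73 cases. The only internal test that section 5 commits to would hold about 16 at most in expectation. If Kampala sensitivity is estimated there, the 7.2.1 calculation does not describe that analysis, and the exact interval is about 62% to 98% (14/16), against 81% to 96% (72/80) at best from all 1600 infants.

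This rests on three assumptions: the 5% rate, the use of the whole 20% for final testing, and the inference that the hold-out is the analysis set.

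Two stronger readings are not supported:
- A reader might infer that Phase 1 as a whole is too small. The three prediction-model methods in 7.2.1 are separate, do not size the hold-out, and are not contradicted by it.
- A reader might infer that the model will be trained on too few infants, because 1280 is below 1532. That follows only if 1532 came from the mean-error or shrinkage method, which the plan does not say.

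**What to change.** **Preferred.** Replace items 1a and 1c in section 5 with wording such as: *The final model is developed on all Phase 1 infants. Internal performance, including Kampala sensitivity and specificity, is estimated by bootstrap optimism correction or outcome-stratified repeated cross-validation. Tuning, predictor selection, imputation and threshold choice are repeated within each resample, and confidence intervals reflect the resampling.* Keep Phase 3 as the external test. About 80 expected cases then inform the Kampala estimate. All 1600 infants serve development, which exceeds 1532 by 68 (4.25% of 1600) before any loss or missing data.

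The cost is more computing, which is not trivial if neural networks are tuned inside every resample, and the loss of a single untouched Ugandan test set. No extra participants or data are needed.

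**Minimum, if the hold-out is kept.** Stratify it by outcome, use it once and for final testing only, and name it in 4.2 or section 5 as the analysis set for Kampala accuracy. State in 7.2.1 that it is expected to hold about 16 cases at 5%, with an exact 95% interval of about 62% to 98% for 14/16, so that the 1460 calculation does not apply to it. Give the exact interval rather than a symmetric plus-or-minus figure. This costs a few sentences but leaves the precision low.

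**In either case,** state in 7.2.1 the half-width behind 1460 and the method that gave 1532.

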Using machine learning to model early-onset neonatal sepsis risk in Uganda (NeoRisk)

- If attended elsewhere, the mother will be asked the reason for presenting, whether the neonate was admitted to hospital, the main diagnosis, and any treatments given.

Recruitment of the first 160 participants from labour ward (10% of the overall sample) will be treated as a pilot, and both recruitment and data will be reviewed at this point with particular attention to the following aspects:

- Demographic comparison between recruited women and the population attending Kawempe
- Data completion
- Volume of blood culture samples taken
- Loss to follow up rates
- Association between potential risk factors and clinical sepsis, or culture-positive sepsis

After this pilot analysis, the data collection instrument may be adjusted to be more concise if some risk factors appear to have no relationship with neonatal outcomes. Additionally, the recruitment strategy may be adjusted to include women attending antenatal clinics to improve the representativeness of the sample if the pilot sample is significantly different demographically to the general population of pregnant women attending the same study site antenatally. Finally, feedback and staff training will be given as needed to ensure optimal sample volumes and data completeness.

During Phase 1, two separate focus group discussions with 10 participants each will be held with staff from Kawempe Hospital. One discussion will be with senior clinicians, and one with junior clinicians and midwives. The focus groups will be held on site at Kawempe in English. Focus groups are being held in order to complement the quantitative results of this project by highlighting risk factors currently perceived as significant (which should then be a key part of analysis and results dissemination to confirm their usefulness), inform of current diagnostic difficulties to guide future work with the risk stratification model, and provide context for development and communication of the model to maximise its utility. The focus groups will address the following issues:

- Ascertain knowledge and awareness of neonatal sepsis
- Management of neonatal sepsis
- regarding risks and consequences of neonatal sepsis, and
- Current diagnostic strategies and their perceived strengths and difficulties
- Perceptions of neonatal sepsis and how this might affect diagnosis and treatment
- Recommendations to enhance the diagnosis and treatment of neonatal sepsis

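### One 20% reserve is named for both testing and validation and no data are assigned to choosing or tuning the model, so Kampala accuracy is not assured to come from unseen infants

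*Combined protocol and SAP*

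**What the plan says.** - **The reserve.** Section 5, Data analysis, item 1a makes the Phase 1 data a training set "with 20% reserved for testing and validation". It does not divide the two purposes, define validation, or say how and when the reserve is drawn.
- **Model choice.** Item 1b names gradient tree boosting and neural networks, and item 1d adds recurrent networks among other techniques. Item 1d also says: "Determination of the exact machine learning model will depend on the data obtained". It does not say which data. Item 1c mentions bootstrapping only as a possibility, without a purpose. Cross-validation is not mentioned.
- **Outputs.** Section 4.2 lists sensitivity, specificity and predictive values for Kampala as well as Harare. AUC is named only for Phase 3, at the end of section 5.
- **Pilot.** Section 5 states: "Recruitment of the first 160 participants from labour ward (10% of the overall sample) will be treated as a pilot". One item reviewed is "Association between potential risk factors and clinical sepsis, or culture-positive sepsis", after which fields that look unrelated to outcome may be dropped from the data collection form. Nothing keeps these infants out of the reserve.
- **Dates.** Section 5 places Phase 1 in January to July 2024 and then says: "We anticipate Phase 2 will take place between March and September 2024". It does not say whether models are fitted before recruitment ends.
- **Simulated data.** Section 7.2.1 allows simulated training data to be built from existing data if culture-positive sepsis is rarer than planned. It does not say which infants may seed them.

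**The concern.** Three steps need data other than those on which a model's parameters are fitted: choosing between algorithms, tuning them, and setting the cut-off that turns a risk into a positive or negative call. In this plan the 20% reserve is the only Kampala data outside training. If the best performer is chosen on that block and its performance there is then reported, the winner's lucky chance variation is reported along with its merit.

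The Kampala figures matter in their own right. Section 2 presents a culture from every infant as the advance over earlier models, and Harare's primary outcome is clinician diagnosis. The Kampala reserve is therefore the only planned unseen check against culture in all infants. An inflated value there would also make any drop in Harare harder to read.

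The pilot raises a smaller version of the same question, because outcome associations in infants who may later sit in the reserve can already have shaped the predictor list.

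**Working it through.** **Inputs from the documents.** Phase 1 size 1600 (section 7.2.1: "hence the size of 1600 should be sufficient even with some loss to follow up"); culture-positive rate 5% and sensitivity 90% (section 7.2.1); reserve 20% and pilot 160 (section 5).

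**Inputs assumed here.** True AUC 0.75 for every candidate; correlation between candidates' scores 0.5 to 0.9; 2 to 10 candidates. The documents give none of these.

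**1. The plan's own figures.** The pilot share reproduces: 160/1600 = 10%. The minimum of 1460 uses N = z² × Se × (1 − Se) / (d² × prevalence), but the half-width d is not stated. Solving for it gives d = √(1.96² × 0.09 / (1460 × 0.05)) = 0.069. With d = 0.07, N = 1411, or 71/0.05 = 1420 if cases are rounded up. So 1460 fits a half-width of about 7 points but cannot be rebuilt from the stated inputs alone.

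**2. Size of the blocks.** Reserve: 0.20 × 1600 = 320 infants, 320 × 0.05 = 16 cases, 304 non-cases. Training: 1280 infants, 64 cases.

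**3. Optimism if the reserve both selects and reports.** Scores were simulated as normal, with cases shifted by √2 × z(0.75). K equally good candidates were scored on the same 16 cases and 304 non-cases and the highest AUC was kept (1500 repeats per setting). Mean excess over 0.75:

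| Candidates | correlation 0.5 | 0.8 | 0.9 |
|---|---|---|---|
| 2 | 0.027 | 0.018 | 0.011 |
| 5 | 0.052 | 0.032 | 0.023 |
| 10 | 0.068 | 0.047 | 0.035 |

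For scale, the standard error of an AUC of 0.75 in this reserve is about 0.07 (Hanley-McNeil).

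**4. A measure the plan lists for Kampala.** Suppose the cut-off is the highest one that still catches 15 of the 16 reserve cases. Observed sensitivity is 15/16 = 94%. The cut-off sits at the second-lowest case score, so the expected share of future cases below it is 2/(16 + 1) = 11.8%, and expected true sensitivity is 15/17 = 88%. Simulation agrees (mean 88%, 95% range 70% to 98%). This gap of about 6 points does not depend on the assumed AUC.

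**5. If the reserve is halved instead.** Each half has 160 infants and 160 × 0.05 = 8 cases. Wald half-width for 90% sensitivity: 1.96 × √(0.09/8) = 21 points, against 1.96 × √(0.09/16) = 15 points for the whole reserve. Wilson 95% intervals: about 56% to 98% against 67% to 98%.

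**6. Pilot overlap.** A simple random reserve would take 0.20 × 160 = 32 pilot infants, 32/320 = 10% of it. The whole pilot holds about 160 × 0.05 = 8 cases, of which about 8 × 0.20 = 1.6 would fall in the reserve.

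**7. Phase overlap.** If accrual were constant over January to July 2024 (213 days), 60/213 × 1600 ≈ 450 infants would be recruited by the start of March. That is how many could be modelled early; the documents do not say that any will be.

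**The case against.** The strongest reply is that the plan never says the reserve will be used for tuning. Elsewhere, in objective 4 of section 4.1 and in the Phase 3 text, validation means checking performance. Read that way, testing and validation are one job done on reserved data. A later sub-split is also possible. This stands. A reader might infer that the plan tunes on its test set and that the Kampala accuracy is therefore overstated, but the documents support neither statement. They fail to rule the practice out.

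Other replies also have weight:

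- Equally good candidates are the pessimistic case, because real differences in quality shrink selection bias. Item 1b names two families, so the 2-candidate row is closest to the text; larger counts would arise from tuning variants, which the plan does not enumerate.
- AUC is not a named Kampala output, so step 3 only illustrates scale. Step 4 covers a listed measure.
- A reader might take the overlapping dates to mean that early infants are modelled and then tested. That is an inference: a March start fits writing code equally well, and the study summary and the data protection appendix give other periods.
- Harare is a separate dataset to which the finished model is applied, so this re-use does not affect it. The two sites also differ in outcome and planning rate (5% culture-positive, 16% clinical), so a difference between them could never be read as pure loss of transportability.

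What remains is that no Kampala data are assigned to selection and no rule locks the reserve. Harare cannot replace the missing check, because its primary outcome is not culture.

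**Conclusion.** The point holds as a conditional one: the plan does not separate selection from testing, so it does not assure that the Kampala sensitivity, specificity and predictive values come from unseen infants.

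- If the reserve serves both purposes, the values would be optimistic: about 0.01 to 0.03 in AUC for 2 candidates and 0.02 to 0.05 for 5, under the assumptions in step 3, or about 6 points of sensitivity for the cut-off rule in step 4.
- If the reserve is halved, the bias goes but about 8 cases remain for testing.
- The pilot leak is probably small, and early modelling is only inferred from dates.

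All case counts assume 1600 infants with a usable culture and a 5% rate. Missing cultures would lower them; no rate is given. The change is worth making before Phase 2 because it helps under either reading of the text.

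**What to change.** In section 5, Data analysis, state that:

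1. Algorithm choice, tuning and cut-off selection use repeated stratified cross-validation (or bootstrap) inside the 80% training data only, where about 64 cases are expected.
2. The full 20% reserve is opened once, for the final frozen model including its cut-off. Give the rule and date for drawing it.
3. The 160 pilot infants, and any infant used in modelling before the reserve is drawn, belong to training. To keep 320 in the reserve, draw them from the other 1600 − 160 = 1440 (320/1440 = 22%), or from fewer if early modelling takes place.
4. Reserve infants do not seed the simulated training data contemplated in section 7.2.1.

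The cost is analysis wording, computing time and possibly a lower reported Kampala accuracy. The reserve would also contain no pilot-period infants. If recruitment changes after the pilot, as sections 5 and 7.3.1 allow, the report should note that training and reserve then differ in period and possibly in case mix. No new data collection is needed.
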